8. STATISTICAL CONSIDERATION AND DATA ANALYSIS PLAN

8.1 Analysis of baseline characteristics

To determine the demographics and characteristics of the patients in the two arms the following data will be collated and summarised:

- Age, Gender, Weight, Height, and BMI
- Smoking status and alcohol consumption

•

- Significant comorbidities, including peripheral arterial disease, heart failure, pretibial oedema.
- Aetiology, chronicity, and location of wound chronicity relies on patient recall.
- Presence of diabetes, and if so length of having condition (chronicity)
- Neuropathy status, ischaemia status
- Offloading of the foot ulcer (yes/no)
- HBa1c (measured within last 6 months; only if diabetic)
- Ankle-Brachial Index value (if available and measured within last 12 months)
- Wound infection or not (or infected at any stage of participation)

8.2 Primary outcome statistics

The primary objective for this pilot study is the feasibility of conducting a larger scale randomised controlled trial. The secondary outcome statistics (on efficacy) will aid to inform the success of this pilot study and will therefore inform whether a larger scale trial is indicated. This will be based on signs of clinical effectiveness, positive patient feedback on the intervention, positive changes in foot ulcer related quality of life, recruitment to time and target, low attrition rates, minimal data queries and lack of or low number of adverse events. If the effect size of the Natrox intervention pedal is large enough, then this pilot trial may possibly provide a definitive answer concerning its clinical effectiveness.

The following descriptive statistics will be reported on:

- Number of patients screened
- Number of patients eligible/ineligible, and percentage of patients consented into the trial

Number of patients completed the trial/discontinued (plus reasons if discontinued)

Patient feedback on the use and comfort of the Natrox device, and compliance with the prescribed therapy regime will be summarised in tabular and graph format.

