Primary objective / outcome measures	To assess the feasibility of conducting a full RCT in the future - Participants' experience of and compliance with Natrox oxygen therapy - Recruitment and attrition rates, willingness of patients to consent and to be randomised, response rates to questionnaires, and degrees of missing data - Testing of eligibility criteria and ability/willingness of clinical staff to partake in recruitment and follow-up of participants - Adequacy of duration of follow-up (e.g. in relation to foot ulcer healing) - Appropriateness of inclusion/exclusion criteria and outcomes measures (both clinical and patient-reported). Descriptive assessment of wound size and characteristics (wk 0,3,6,9,12) Percentage 'wound healed' vs week 0 Percentage healing of the wound vs week 0 Change in semi-quantitative PUSH ulcer size score vs week 0 - SINBAD score (DFU only) vs week 0 - Wound closure status - Clinical characterisation of wound (erythema, purulence, odour, patient-reported pain) Safety of applied oxygen therapy in comparison to standard care arm (ongoing): - Wound infection incidence - Need for secondary interventions, such as surgery				
Secondary objectives / outcome measures					

	Patient-reported outcome measures (wk 0, 6, 12) - (Wound related) Quality of life scores (EQ-5D-5L and CWIQ) - Wound pain scale
Patient population	A total of 24 eligible participants will be randomised to receive either standard care or standard care plus Natrox topical oxygen therapy. Patients to be aged eighteen or over, with measurable foot ulcer present for at least two weeks, treated in podiatry clinic. Participants must have the capacity to provide informed written consent and complete patient reported outcome measures, and be willing and capable to wear the Natrox device.
	All participating patients – whose index wound has not healed by 50% or more in first four weeks of screening whilst in the study and under care of podiatry team - will be randomised for the trial phase. Those patients who were enrolled and whose foot ulcer healed 50% or more complete the study at the end of the four-week screening phase.
	In summary, of those participants whose wound does not heal 50% in four-week screening phase: - 12 Patient will receive treatment as usual (TaU) - 12 Patients will receive TaU plus adjunct Natrox topical oxygen therapy
	Randomisation will be stratified for ulcer size, with cut-off PUSH score of up to and including 5, and 6 and above.

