6. SUBJECTS

6.1 Anticipated number of research subjects

This concerns a feasibility trial, and therefore the results from this study should inform a potential effect size for Natrox oxygen therapy, and also the degree in variance in wound healing rates (primary clinical outcome). To date, there is not sufficient published data to gain an insight in the effect that Natrox may have on foot ulcer healing. Hayes et al (2017) previously conducted a pilot study involving 10 DFU patients. In that study, there was no screening phase and Natrox treatment lasted for eight weeks. At the week 8 time point, a mean healing vs baseline of 51% was achieved.

Guidance from a publication by Julious (2005) advises the use of 12 participants per treatment arm, and this approach will be taken here (see Table 3). Patient withdrawal rates before week 12 are not known at present and measuring this will be a primary aim

Table 3, sample size numbers required, based on hypothetical differences between published data and study outcomes

	Standard (control) arm	care	Standard care plus Natrox oxygen therapy arm
Patients (n)	12		12

Since this concerns a randomised controlled trial, albeit in the shape of a feasibility study, reprting will be done in line with CONSORT guidelines (Schulz, Altman & Moher 2010). The number of patients screened but who did not meet the inclusion criteria or who declined to participate will be recorded, as will any patients who are lost to follow-up (Appendix 2).

Since this study involves a screening period, after which patients may not qualify for Natrox intervention, it is anticipated that more than 20 patients will be recruited. The patient attrition rate (withdrawal and loss to follow-up) will also be recorded, since this involves a study with at multiple visits, albeit incorporated into standard clinical appointments. Patients will be recruited from the adult (age 18+) population routinely seen by the evaluating clinical staff members.

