6.1.1 Randomisation

Following written consent at -4 weeks, participants will be observed for four weeks to establish healing rate. At the end of four weeks, patients are only eligible for the intervention phase if their wound has healed <50% in the preceding four weeks. At this point, week 0, participants are allocated at random to the control or Natrox intervention group, using a randomised sequence from the freeware randomisation programme, see https://www.randomizer.org/. The randomisation is stratified for ulcer size, with PUSH score of 5 or less, and 6 or above as the cut-off. This size has been determined as the average size of a presenting foot ulcer previously (Zimny et al, 2002).

Sequential envelopes with each next randomisation allocation will be used to achieve concealment and these will be kept in the research department. The researcher will then inform the regular healthcare professional for the participant in question, and the participant themselves, which treatment they've been allocated to. The researcher will dispatch a Natrox device to the clinic where the participant will be seen. At this stage the continuous Natrox treatment (though disconnection for washing or changing of clothes is allowed) will commence.

As the study involves administration of a visible device, it is not possible to achieve blinding for the participants nor the researchers – it is recognised that this increases the risk of bias. Since the device has an indicator to show it is functioning, applying a sham device is not possible either on this occasion.

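### Section 8.2 lets a large observed effect in this 24-patient, open-label pilot count as a definitive answer on effectiveness, which the design cannot support

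*Protocol*

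**What the plan says.** Section 8.2 (Primary outcome statistics) opens by naming feasibility of a larger trial as the primary objective. It then gives the secondary efficacy statistics a part in judging whether the pilot succeeded and whether a larger trial is indicated: "This will be based on signs of clinical effectiveness, positive patient feedback on the intervention", followed by quality of life, recruitment, attrition, data queries and adverse events. That makes seven considerations, with no stated weights. The paragraph ends by saying that, given a large enough effect, "this pilot trial may possibly provide a definitive answer concerning its clinical effectiveness". It does not say how large is large enough.

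Other sections describe a design with a narrower purpose:

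- **Size.** The protocol summary states: "A total of 24 eligible participants will be randomised to receive either standard care or standard care plus Natrox topical oxygen therapy". Section 6.1 takes the number from a published pilot rule that "advises the use of 12 participants per treatment arm". The caption of Table 3 mentions hypothetical differences, but the table gives none.
- **Effect size.** Section 6.1 says that "the results from this study should inform a potential effect size for Natrox oxygen therapy" and that "there is not sufficient published data to gain an insight in the effect that Natrox may have on foot ulcer healing".
- **Blinding.** Section 6.1.1 says that neither participants nor researchers can be blinded and that a sham device is not possible. It adds that "it is recognised that this increases the risk of bias".
- **Assessment.** Section 5.5 has the treating podiatrist measure ulcer size and score PUSH. Under section 3.2 a podiatrist also applies the device.
- **Analysis.** Section 8.3 makes week 12 the main time point for ulcer area and considers the sample too small for Cox regression.

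**The concern.** The last sentence of that paragraph in section 8.2 gives advance permission to treat a large observed effect as settling the question of effectiveness. Two features of the design stand against that. In a sample this small, the results that reach significance are mostly those in which chance has inflated the effect. And no observed effect, however large, removes the bias that can enter when the unblinded treating podiatrist measures the outcome. Because no threshold is given, whether the effect was large enough could be judged after the data are seen.

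The same paragraph lets efficacy signals feed the decision on a larger trial without saying how such imprecise results should be read. A chance or biased positive could be reported as proof. An absent signal could be taken as a reason not to proceed although the data barely bear on the question.

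**Working it through.** **The plan's own figure.** 12 + 12 = 24 is consistent. The 12 cannot be reproduced from a power formula, because the protocol gives no alpha, power, effect size or SD. The check is therefore what 12 per arm can support.

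**Inputs.**
- n = 12 per arm (section 6.1).
- Two-sided alpha 0.05: assumed.
- Control healing by week 12 of about 10%: section 2 gives this for diabetic foot ulcers not half healed after four weeks. Using it for all randomised ulcers is an assumption, since non-diabetic ulcers are also eligible. Section 2 gives 24% for diabetic foot ulcers on average, used here as an alternative.
- SD of percentage area change: not given. A range of 30 to 60 points is assumed.

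**1. Continuous outcome, t-test with 22 degrees of freedom.** The standard error of the mean difference, in SD units, is √(2/12) = 0.408.
- 95% CI half-width = t(0.975, 22) × 0.408 = 2.074 × 0.408 = 0.847 SD. With an SD of 30 to 60 points this is about 25 to 51 percentage points of area change.
- Power from the noncentral t with noncentrality d/0.408: 22% at d = 0.5, 47% at d = 0.8, and 80% at d = 1.197. With 10 or 9 evaluable per arm, the difference detectable with 80% power rises to 1.32 or 1.41 SD.

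**2. Complete healing.** Power was found by enumerating all pairs of binomial counts at 12 v 12 and applying the chi-squared test without continuity correction.

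| Control | Device | Power |
|---|---|---|
| 10% | 30% | 20% |
| 10% | 40% | 39% |
| 10% | 50% | 60% |
| 10% | 60% | 79% |
| 24% | 50% | 28% |

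With 1 of 12 controls healed, significance needs at least 6 of 12 on the device (p = 0.025); 5 of 12 gives p = 0.059.

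**3. What a significant result would mean.** In 200,000 simulated trials with normal outcomes and a true d of 0.5, the significant results overstated the effect about 2.1-fold on average.

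**4. What a missing signal would mean.** The same binomial enumeration gives:
- Truth 10% v 20%: control has more healed patients in 15.8% of trials, and the arms tie in 18.5%.
- Truth 10% v 30%: control ahead in 6.0%, tie in 9.5%.

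**5. Bias.** None of these figures allows for unblinded assessment. They describe chance alone.

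**The case against.** The sentence is conditional and doubly hedged. It plans no test and sets no success rule, and it follows a clear statement that feasibility is primary. A very large effect could reach significance: power is 79% at 10% v 60%. These points lower the severity but do not rescue the sentence. Its condition has no threshold, and significance would not deal with unblinded measurement by the treating podiatrist.

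Four stronger readings are tempting, and the documents do not support them.

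- **Progression rests on efficacy.** Efficacy is one of seven considerations. Being listed first gives it no stated weight or veto, and efficacy is a declared secondary objective (section 4.2). Removing it from the decision altogether would go beyond the fault.
- **Many unadjusted tests make a false positive likely.** Counting every outcome at every visit could give 19 tests, and 1 − 0.95^19 = 62%. But that count is an inference, the tests are far from independent, and section 8.3 names week-12 ulcer area as the main comparison. Nor does every test run at 5%: the healed comparison at 10% v 10% rejects only 1.5% of the time. Multiplicity control may also sit in a statistical analysis plan that is not at hand.
- **The sample size is wrong.** Twelve per arm is reasonable for feasibility and for estimating variance. The fault is the inference drawn from it.
- **Numerical progression criteria are missing.** They too may be in the analysis plan.

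**Conclusion.** Wrong as written; should be fixed. The protocol allows for a definitive conclusion on effectiveness from a design that cannot yield one. The sample was not sized for efficacy, the effect size is something the trial is meant to inform, treatment is open, and the treating podiatrist measures the main clinical outcome.

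The chance element alone is large: conventional power is reached only at about 1.2 SD, or roughly 10% v 60% healed. The imprecision also works the other way. At a true 10% v 20%, about a third of trials (15.8% + 18.5% = 34.3%) would show no advantage in healed count, of which just over half are ties.

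The figures rest on an assumed two-sided alpha of 0.05 and on applying the 10% rate for slow-healing diabetic ulcers to all control patients. At 24% control healing the conclusion is the same. The problem does not affect conduct, participants or the feasibility objective; it affects what the trial may claim and how its efficacy results are read.

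**What to change.** In section 8.2:

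1. Delete the sentence on a definitive answer.
2. State that efficacy comparisons are reported as estimates with 95% CIs to plan a larger trial, and that no effectiveness claim will be made from this trial.
3. Keep signs of effectiveness among the considerations if wished, but state that they are read from those estimates and intervals, so that neither a significant nor a non-significant result alone decides progression.

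The cost is a few sentences in one section. No patients, visits or data are added. The sponsor gives up only a claim that the design could not deliver.

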5.3 Consent

Those eligible will be approached and provided with an information pack and consent form, which will be signed to indicate that informed consent has been given. Patients will be given ample time to consider taking part, more than 24 hours if they wish. The direct healthcare professional will first approach a patient about the study, and after verbal consent by the patient the healthcare professional themselves or a member of the research team can go through the informed consent process. If there is insufficient time in clinic, the podiatrist or delegated research can follow-up with a phone call to the patient to ensure they understand the PIS and have had opportunity to ask any questions they may have.

The start of the 4-week screening period is the date of written consent being obtained.

Participants will receive no incentives and consent will be regarded as a process and not a one-off event. Participants are free to withdraw from the study at any time without the need to give any reasons for withdrawal. Their standard of care will not be affected by either declining to participate in the study or withdrawing during participation. Data collected up to the date of withdrawal will be retained for analysis. Only one questionnaire will be presented to patients who withdraw or complete early, the patient experience questionnaire (still voluntary for patients to complete or not).

5.4 **Recruitment**

Participants will be enrolled for a total of 16 weeks, see Table 2, or until ulcer healing has been achieved (if the latter occurs then they will still be followed up according to the study schedule in terms of patient-reported outcome measures). All participants will have demographic and medical data obtained and a number of baseline and follow-up measures.

Table 2. Overview of study measurements

Weeks	-4	0*	3*	6*	9#	12~
Clinical characterization of wound	Х	Х	Χ	Х	Х	Χ
Ulcer size (Coloplast grid or suitable equiv)	Χ	Χ	Χ	Χ	Χ	Χ
PUSH score	Χ	Χ	Χ	Χ	Χ	Χ
SINBAD DFU grading score (DFU only)	Χ	Χ	Χ	Χ	Χ	Χ
Wound status (closed/recurrence/infection)		Χ	Χ	Χ	Χ	Χ
photo of wound (if possible and consented by patient)		Χ		Х		Х
QoL CWIQ		Χ		Χ		Х
QoL EQ-5D-5L		Χ		Х		Χ
Experience questionnaire (Natrox only)						Χ

^{*} Up to 1 week early or late

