The Pressure Ulcer Scale for Healing (PUSH) tool is a standardised method of assessing and monitoring the severity and healing of both pressure ulcers and venous leg ulcers, and is also applied for foot ulcers (Stotts et al, 2001; Ratliff & Rodeheaver 2005). The Pressure Ulcer Scale for Healing (PUSH) is a valid, responsive, evaluative tool to monitor and document wound progress of foot ulcers (Hon, 2010). Findings also suggest that total PUSH scores predict time-to-heal for foot ulcers (Gardner 2011).

The SINBAD grading score was developed and validated for use in patients with diabetes (Ince etal, 2008).

5.5 **Follow-up**

Patients are in the study for a period of 16 weeks, of which 4 weeks are screening and 12 weeks are intervention or control. Thereafter, the patient will be followed up as they would be in normal clinical practice. During and after the trial, clinical staff will redress the wound as per routine care, and during the trial they will conduct the measurement of the foot ulcer (grid measurement tool, SINBAD grading and PUSH score). The researcher will be in attendance at week -4, 0, 3, 6, 9, and 12 of study participation to consent the patient and conduct/collect the study participant questionnaires.

The clinical outcomes and scores, ie characterisation of wound and SINBAD (both part of standard clinical practice), plus ulcer size and PUSH score are conducted by the treating podiatrist. Furthermore, microbiological swabbing of the wound is also performed by the podiatrist.

The patient-reported scores, wound-related quality of life score (Cardiff wound index), generic quality of life score (EQ-5D-5L) and end-of-trial experience survey (Natrox wearers only) are all competed by the patient and the researcher can support the patient if they indicate that they require some assistance (the researcher will not prompt patients to select a certain answer).

[#] Up to 2 weeks early or late

[~]Up to 3 weeks early or late (in exceptional circumstances, wk 9 and 12 visit can be combined if wk 9 visit is late and wk 12 visit can only take place early)

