5.6 Outcome measures

5.6.1 **Primary outcome measures**

To assess the feasibility of conducting a full CRT in the future, the primary outcome measures are mainly:

Trial-related outcome measures

- Participants' compliance to and satisfaction with Natrox device
- Recruitment and attrition rates, willingness of patients to be consented and randomised, response rates to questionnaires, and degrees of missing data
- Testing of eligibility criteria and ability/willingness of clinical staff to partake in recruitment of participants
- Ability of sites and clinicians to recruit and randomise patients
- To assess any training requirements
- Adequacy of duration of follow-up (e.g. in relation to foot ulcer healing)
- Fitness for purpose of data collection methods including across and between care settings
- Suitability of inclusion/exclusion criteria and outcome measure tools.
- Adverse events

5.6.2 **Secondary outcome measures**

This study also aims to record wound characteristics and patient-related outcomes measures, as well as safety endpoints and microbiology assessments.

The main clinical outcome for this trial will be the efficacy of the Natrox oxygen therapy in terms of wound healing. For all participants, wound healing will be measured

Foot ulcer size, measured with wound grid tool (week -4, 0, 3, 6, 9, 12). Measured in % change in cm² - between week 0 and weeks, 3, 6, 9, and 12 respectively

Assessment wound size and characteristics (wk 0,3,6,9,12)

- Clinical characterisation of wound (incl. erythema, purulence, odour), wound closure status
- PUSH and, if applicable, SINBAD DFU score

Extended safety outcome measures, general and in relation to applied Natrox (ongoing):

- Wound infection incidence
- Need for secondary interventions (incl. need for surgery, admission to hospital, iv antibiotics)
- (indirect) reaction to Natrox, the web itself or oxygen therapy
- Any other adverse events

Patient-reported outcome measures (wk 0, 6, 12)

- Quality of life score (EQ-5D-5L and Cardiff Wound Impact Questionnaire)

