Even if Natrox therapy is discontinued, paarticipants will still be followed up at the indicated time points and asked to complete PROMs questionnaires, plus microbiology samples will be taken at the predetermined time points.

Use of intravenous antibiotics during trial

The use of topical or oral antibiotics is not an exclusion criterion and the initiation of said types of antibiotics does not necessitate withdrawal of the patient from the ANODE trial. However, the use of intravenous antibiotics specifically for the wound is an exclusion criterion. Therefore, if iv antibacterial treatment is required, the patient will be taken off Natrox treatment if they were allocated to that arm. Participants will still continue to be followed up to collate outcome measures in line with the protocol timelines. For participants in the treatment as usual arm the same approach will be taken, though there is obviously no requirement to withhold the Natrox treatment.

Study outcome measures will still be obtained where possible, in line with regular study timelines, and any reasons for Natrox therapy discontinuation will be recorded.

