8.3 Secondary outcome statistics

The clinically-related objective for this trial is the healing rate of the foot ulcers, as assessed by tracing the wound using a Coloplast measuring grid, or an equivalent performance-equal measuring tool.

The average difference between time points and baseline (week 0) will be calculated per group, 12 weeks being the primary endpoint but weeks 3, 6 and 9 will also be analysed. To compare the groups, the Mann-Whitney U-test will be applied (data will be tested for normal distribution and if applicable, t-test will be applied).

The average change in healing at 12 weeks between the Natrox cohort and the control cohort within the study will be compared using the Mann-Whitney U-test or, if data normally distributed, t-test. Application of this analysis will depend on sample size of control cohort.

The average baseline demographics for participants in each group (Natrox and control) will be described and compared to ascertain the distribution of participants' data for: sex, age, HbA1c level, baseline wound size (cm2), PUSH score, SINBAD DFU grading score (if applicable), EQ5-5D-5L score, CWIQ score, duration of wound (weeks), neuropathy status, ischaemia status.

Other clinical parameters will be recorded too, since they are known to be significantly associated with non-healing of foot ulcers: diabetes status, peripheral arterial disease, heart failure, pretibial oedema (Prompers et al, 2008)

The Chi-squared test will be applied to the above cross-tabulation to determine if there is a significant difference in distribution of treatment outcome in terms of 'status wound healed' (Natrox vs control).

To evaluate the wider effects of the Natrox topical oxygen therapy regime on foot ulcer healing, the following parameters will be compared (median difference between week 0 and different follow-up time points):

- PUSH score
- SINBAD grading score
- Visual analogue pain score
- EQ5-5D-5L score
- CWIQ score

To compare, Mann-Whitney U-test between cohorts, since data is ordinal.

The sample size in this feasibility trial is too small to conduct Cox proportional hazards regression analysis to investigate the role of the dressing regime choice and other in wound healing rates.

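### Device compliance is a primary outcome, but the protocol schedules no record of device use during treatment; the pain score and swab time points also need aligning across sections

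*Protocol*

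**What the plan says.** **Compliance.** The first item in the section 5.6.1 list of primary outcomes is "Participants' compliance to and satisfaction with Natrox device", and the protocol summary likewise opens its list with "Participants' experience of and compliance with Natrox oxygen therapy". The lay summary (section 1) gives the lack of evidence on compliance rates as one reason for the trial. Section 8.2 promises that "compliance with the prescribed therapy regime will be summarised in tabular and graph format".

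The text on collecting device information is thinner:

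- Table 2 (section 5.4) has one device-related row, "Experience questionnaire (Natrox only", marked at week 12 only.
- Section 5.3 also offers this questionnaire, on a voluntary basis, to patients who leave or finish ahead of time.
- Section 3.2 has staff ask at every clinic visit whether the device has caused problems.
- Section 6.3.2 has the reason recorded when the device is stopped.

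**Pain.** Section 8.3 compares the arms on change from week 0 in a "Visual analogue pain score". The summary lists a wound pain scale at weeks 0, 6 and 12.

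**Microbiology.** Section 5.5 says that "microbiological swabbing of the wound is also performed by the podiatrist", section 5.6.2 names microbiology among the things to be recorded, and section 6.3.2 says that "microbiology samples will be taken at the predetermined time points".

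**The concern.** Sections 3.1 and 6.1.1 describe continuous therapy. Patients may disconnect the device to wash or change clothes, and they handle the daily changeover of power themselves. Use can therefore vary from day to day. A table and graph of compliance need a quantity recorded during treatment, such as days worn or time disconnected, and the protocol asks nobody to record one.

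An SAP can decide how to summarise wear data, but it cannot supply data that were not gathered. Whether patients will wear the device is among the main things this feasibility trial should tell the planners of a larger one.

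The pain and swab points are smaller. A site working from Table 2 and section 5.5 would find no pain scale among the instruments to hand out, and would not know at which weeks to swab.

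**Working it through.** No figure in the protocol is in dispute, so the check sets the schedule beside the outcome and analysis sections.

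**Step 1. Rows of Table 2.** There are nine: clinical characterisation, ulcer size, PUSH, SINBAD, wound status, photo, CWIQ, EQ-5D-5L and the experience questionnaire. None is named as device use, pain scale or swab.

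**Step 2. What other sections supply.**

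| Item | Outcome or aim | Result promised in section 8 | Collection text outside a named Table 2 row | What is left open |
|---|---|---|---|---|
| Compliance | Primary (summary, 5.6.1) | Yes (8.2) | Question about problems at visits (3.2); reasons for stopping (6.3.2) | Definition, unit, instrument, timing |
| Pain score | Patient-reported outcome (summary) | Yes (8.3) | Scale at weeks 0, 6, 12, and pain within clinical characterisation (both in the summary) | Missing from Table 2, 5.5 and the 5.6.2 patient-reported list; called a visual analogue score only in 8.3 |
| Swabs | To be recorded (5.6.2) | No | Taken by the podiatrist (5.5); fixed time points implied (6.3.2) | The time points themselves |

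**Step 3. What the questionnaire can carry.** Its items are not described, so whether it asks about wear is unknown. If it does, it gives one report per patient. The week-12 visit may fall up to 3 weeks early or late, so the report looks back over 12 − 3 = 9 to 12 + 3 = 15 weeks. The question about problems does not measure wear, and a reason for stopping does not describe use before the stop.

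**Step 4. What existing visits could carry.** Section 3.2 requires a podiatry visit at least every 7 days. Over 12 weeks that is about 12 visits per patient, and 12 patients × 12 visits = 144 possible records in the Natrox arm. This assumes weekly attendance, no early healing and no dropout, so it is a guide to scale only.

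**Step 5. Who would be counted.** Section 5.3 keeps data gathered before withdrawal, while section 6.3.1 excludes them. Until these are reconciled, it is unclear whether a withdrawn patient's device information enters the compliance summary.

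**The case against.** Table 2 is titled an overview. Adverse events, demographics and reasons for stopping are also absent from it, yet other sections collect them. Case report forms are not shown and may hold a device-use line. This stands: absence from the table does not prove that an item goes uncollected. What remains is that the protocol nowhere requires a device-use record, so it does not secure one for a primary outcome.

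A reader might infer that patients who stop the device vanish from the compliance figure and inflate it. The documents do not support that. Those who leave or finish early are offered the questionnaire, patients whose device is stopped stay in follow-up (6.3.2), and section 8.2 reports discontinuations with reasons. The documents also do not show that recall would overstate wear; the supportable criticism is that a single look back is a coarse measure.

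A reader might also infer that the pain comparison has no data behind it. The summary schedules a pain scale at weeks 0, 6 and 12 and places patient-reported pain within clinical characterisation, which Table 2 covers at every listed week. This is a mismatch between sections.

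For swabs, section 8 promises no microbiology result, so no promised analysis fails. The idea that swabs would be taken as staff see fit is conjecture against the wording of 6.3.2, which refers to set time points.

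Finally, compliance reporting is descriptive in a 24-patient feasibility trial, and the considerations in section 8.2 for going on to a larger trial do not name compliance. That lowers the severity. It does not remove the gap, because compliance is still a listed primary outcome.

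**Conclusion.** The point holds for compliance and should be fixed. A primary outcome has no stated definition and no scheduled measurement during treatment. On the protocol's own text it would rest on at most one retrospective report per Natrox patient over 9 to 15 weeks, together with reasons for stopping. Weekly recording at existing visits could give about 12 reports per patient.

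The pain score is an inconsistency to reconcile, and the missing swab time points are a minor omission. It would go too far to say that any of the three is never collected, or that the promised results cannot be produced.

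The conclusion assumes that no case report form or other trial document already requires a device-use record. If one does, the remaining task is to cite it in the protocol.

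**What to change.** 1. **Compliance.** Add a Natrox-arm device-use row to Table 2, completed by the podiatrist at each of the visits already required at least every 7 days. Record days worn since the last visit, approximate time disconnected, battery changes, and the date and reason for any stop. Say in 5.6.1 or 8.2 which of these defines compliance. Section 3.1 speaks of swapping batteries daily and 3.2 of changing the box every 24 hours; reconcile the two so that the form counts the right thing.
2. **Pain.** Add the pain score to Table 2, 5.5 and the 5.6.2 patient-reported list at weeks 0, 6 and 12 in both arms, and use one name for it throughout.
3. **Swabs.** State the swab time points, or delete the swab text from 5.5, 5.6.2 and 6.3.2.

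**Cost.** One short amendment and a few form lines. At an assumed one minute per visit, 144 visits take 144 minutes, about 2.4 hours across the Natrox arm.

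**Limit.** If recruitment followed Table 1 (October 2019 to July 2022, 33 months), 27 of those months had passed by the date of this version in January 2022. The new row cannot recover wear data for patients already treated, so their compliance should be reported separately, with its source stated.
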